7.3.1.2 Analysis of Covariance (ANCOVA)

An ANCOVA model will be used to evaluate the difference between the RMP-A03 and RMP-A03 vehicle treatment groups in change from baseline in pterygium hyperemia grading at each post-baseline visit. This analysis will use LOCF for the mITT Analysis Set, and observed data for PP Analysis Set.

The model will include terms for treatment, and actual baseline pterygium hyperemia grading [REDACTED] will be adjusted in the model as a continuous covariate. The LSM and two-sided 95% CI will be presented for each treatment group. Additionally, the difference between

each RMP-A03 dose level and RMP-A03 vehicle will be calculated, along with the two-sided 95% CI.

The following is reference code for this analysis:

A large black rectangular redaction box covering several lines of text, likely the reference code mentioned in the preceding sentence.

7.3.2 Pterygium Characteristics Analysis

To evaluate the secondary and exploratory efficacy endpoints, change from baseline in pterygium characteristic at Day 28, and Day 56 and Day 84, respectively, baseline, post-baseline, and change from baseline values for pterygium corneal encroachment, and pterygium length in the study eye will be summarized by treatment group and visit. To assess the size of pterygium at limbus, the number and percentage of subjects within each level of clock-hours, and T Grading System will be summarized by treatment group and visit. The denominator will be the number of subjects with non-missing values for the visit.

Change from baseline for pterygium corneal encroachment, and pterygium length in the study eye will be analyzed using the same ANCOVA and MMRM models as the primary analysis.

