### **9.8.2. SECONDARY EFFICACY ANALYSES**

The secondary efficacy endpoint will evaluate change from baseline in pterygium characteristics on day 28 as defined by pterygium length, encroachment onto the cornea, and size at limbus.

Summaries of pterygium width, length, and area will be provided by visit and by treatment group. The secondary endpoint will be analyzed in the same manner as for the primary endpoint.

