4.2.2 Secondary Efficacy Endpoints

- Change from baseline in pterygium characteristics at Day 28
 - length
 - encroachment onto the cornea
 - size at limbus

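### Size at limbus is a declared change-from-baseline secondary endpoint, but SAP 7.3.2 plans only counts per clock-hour level for it, and SAP Section 8 does not declare the departure

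*SAP*

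**What the plan says.** **Endpoint.** SAP 4.2.2 defines the secondary endpoints as "Change from baseline in pterygium characteristics at Day 28" and lists three characteristics, the third being "size at limbus". Protocol 8.1 gives the same list. Protocol 9.8.2 describes the secondary endpoint "as defined by pterygium length, encroachment onto the cornea, and size at limbus".

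**Analysis promised in the protocol.** Protocol 9.8.2 states: "The secondary endpoint will be analyzed in the same manner as for the primary endpoint". Protocol 9.8.1 sets out that manner: an MMRM, each dose compared with placebo, least squares means, and differences with 95% confidence intervals.

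**Analysis written in the SAP.** SAP 7.3.2 has three operative statements:
- Summaries: "change from baseline values for pterygium corneal encroachment, and pterygium length in the study eye will be summarized by treatment group and visit".
- Limbal size: "To assess the size of pterygium at limbus, the number and percentage of subjects within each level of clock-hours, and T Grading System", presented by arm and visit among subjects with a non-missing value at that visit.
- Models: "Change from baseline for pterygium corneal encroachment, and pterygium length in the study eye will be analyzed using the same ANCOVA and MMRM models".

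**Declared departures.** SAP Section 8 lists one change from the protocol: actual baseline hyperemia grading, as a continuous covariate, replaces the stratification category. It applies that model term to every efficacy endpoint.

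**Protocol summary sentence.** Protocol 9.8.2 also says: "Summaries of pterygium width, length, and area will be provided by visit and by treatment group".

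**The concern.** The endpoint is a within-subject change compared between arms. The SAP's output for it is a series of cross-sectional frequency tables, which do not show who moved. If one subject in an arm goes up a clock-hour level while another comes down by the same step, that arm's table is unchanged.

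The mean change could still be worked out by hand from the two visits' counts if the same subjects contribute to both. The spread of the changes could not, so no interval for a between-arm difference can be built from the planned tables.

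Any comparison of limbal size between dose and vehicle would therefore have to be devised later. If that happened after unmasking it would be post hoc, for an endpoint the protocol had named in advance with a stated method. Because Section 8 is silent, a reader of the study report could not tell whether descriptive-only analysis was a decision or an oversight.

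**Working it through.** **1. The plan's own figure.** The only power statement (Protocol 9.5, SAP Section 9) concerns hyperemia grading: 25 completers per arm, difference 0.66, SD 0.7, significance level 0.05, about 90% power.

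- Standard error of the difference = 0.7 × √(2/25) = 0.198.
- 0.66 / 0.198 = 3.33, and 3.33 − 1.96 = 1.37.
- Normal-approximation power = Φ(1.37) ≈ 0.915. The noncentral t gives 0.904 with 48 degrees of freedom and 0.908 with 72.

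The stated figure reproduces, but it says nothing about limbal size. On any continuous change score, 25 per arm at two-sided 0.05 detects (1.960 + 0.842) × √(2/25) = 0.79 SD with 80% power, and (1.960 + 1.282) × √(2/25) = 0.92 SD with 90% power. The documents give no SD for limbal size, so these cannot be turned into clock-hours. The rest of the check is a comparison of text.

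**2. Promised against planned, Day 28.**

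| Secondary endpoint | Change-from-baseline summary (SAP 7.3.2) | MMRM and ANCOVA, dose versus vehicle (SAP 7.3.2) |
|---|---|---|
| Length | Yes | Yes |
| Encroachment onto the cornea | Yes | Yes |
| Size at limbus | No; counts per level by arm and visit | No |

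The protocol promises the right-hand column for all three. Limbal size is the only row without it, and with two doses that removes two Day 28 contrasts.

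**3. Could redaction explain the gap?** The three statements in SAP 7.3.2 read as complete sentences with no blacked-out text, and both the summary and model sentences name their variables. Limbal size is absent from both.

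**4. Is it declared?** No. Section 8 has one entry, on the covariate. Since it applies a model term to every efficacy endpoint, it assumes a model for limbal size that 7.3.2 does not supply. The SAP is thus at odds with itself as well as with the protocol.

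**5. Are the data there?** Yes. Both schedules (Protocol Table 1-2, SAP Table 2) have pterygium assessments of the study eye at Baseline, Day 7, Day 28, Day 56 and Day 84.

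**6. The Protocol 9.8.2 summary sentence.** The endpoint description there lists length, encroachment and size at limbus. The next sentence promises summaries of width, length and area. Only length is common to both.

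**The case against.** **The general rules may cover it.** SAP 7.1.2 defines change from baseline for the whole document, and Section 8 speaks of all efficacy endpoints. This shows the SAP is ambiguous rather than silent. But 7.3.2 is the specific text, names its modelled variables and gives limbal size a different treatment. A programmer would follow it.

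**The data are not lost.** Correct. Counts are shown by arm, and by-subject listings by visit (SAP 7.1.1; Protocol 9.1) let a reader trace individual changes. What is missing is a planned estimate, interval or test.

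**Clock-hours may be too coarse for a Gaussian model.** This may be so. The eligible range is redacted, so the number of levels is unknown. Coarseness is a reason to choose an ordinal or rank method, or to justify description only. It is no reason to leave the choice undeclared.

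**Stronger readings the documents do not support.**
- A reader might put a figure on the precision lost by ignoring baseline. That needs a within-eye correlation, which the documents do not give, and it would compare an unadjusted Day 28 test with an adjusted one when neither is planned for limbal size.
- A reader might infer that width and area have ceased to be endpoints. The current text shows only that they are not listed as secondary endpoints. Other endpoint entries are redacted, and the SAP refers to exploratory endpoints.
- A reader might infer that the protocol plans no summaries of encroachment or limbal size. Protocol 9.8.2 carries over the primary endpoint's treatment, which includes summaries by visit and arm, and the Synopsis promises descriptive summaries of all efficacy data.

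**Conclusion.** The mismatch is real. SAP 7.3.2, followed exactly, produces no change score, no dose-versus-vehicle difference and no confidence interval for a declared secondary endpoint that the protocol says is analysed like the primary. The departure is not listed in Section 8. Its extent is one of three secondary endpoints and both of its Day 28 contrasts.

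This rests on the unredacted wording of 7.3.2 and on the specific section prevailing over the general rules. It needs no assumed variance, correlation or effect size, and no numerical loss can be attached to it from the documents.

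A reader might take it as a defect that must be cured before the trial's results can be relied on. The documents do not support that: the primary objective is safety and tolerability, the study is first-in-human Phase 1/2a, the power statement covers only hyperemia grading, and the primary model is unaffected. It is a should-fix. The Protocol 9.8.2 summary sentence is a smaller wording inconsistency to tidy at the same time.

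**What to change.** Before unmasking, add to SAP 7.3.2 text along these lines:

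> Change from baseline in size at limbus (clock-hours, study eye) will be summarised by treatment group and visit, with a baseline-to-Day 28 shift table. Each dose will be compared with vehicle using the same MMRM and ANCOVA models, including baseline clock-hours in addition to the baseline hyperemia grading term of Section 8. If few clock-hour levels occur, a rank-based or ordinal analysis will be added as a sensitivity check.

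Stating both covariates keeps the addition consistent with Section 8. If the sponsor intends description only, Section 8 should say so and give the reason; that would also resolve the mismatch.

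Align the Protocol 9.8.2 summary sentence with the listed secondary endpoints (length, encroachment onto the cornea, size at limbus). Protocol 12.9 generally requires written IRB approval of amendments, so this can wait for the next amendment or be handled by a note in SAP Section 8.

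Cost: SAP wording and a few extra tables and model runs on data already collected. No new visit or procedure is needed.

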## **9.8.EFFICACY ANALYSIS**

### **9.8.1. PRIMARY EFFICACY ANALYSES**

The primary efficacy endpoint will evaluate change from baseline in pterygium hyperemia grading at Day 28. Summaries of pterygium hyperemia grading will be provided by visit and by treatment group. The primary endpoint of change from baseline in pterygium hyperemia grading at Day 28 will be analyzed by a mixed-effects model with repeated measures (MMRM) using all the data collected post-baseline for the mITT Population. The MMRM model will include model terms treatment, visit, treatment-by-visit interaction, baseline pterygium grading, and baseline pterygium hyperemia grading category used for stratification [REDACTED]. Each dose will be compared with the placebo arm at the 0.05 significance level at each visit. The least squares mean (LSM) for each treatment arm will be calculated together with its 95% confidence interval. In addition, the difference between each active treatment and the placebo will also be calculated together with its 95% confidence interval.

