3.2 Randomization and Masking

Stage 1 is open-label. Subjects in Stage 1 who discontinue before enrollment is complete may be replaced in the study. Replacement subjects will be assigned unique subject numbers.

Stage 2 is double-masked. Approximately 75 subjects with pterygium will be randomly assigned to receive 1 of 3 treatments [REDACTED] in a 1:1:1 ratio. Randomization schedule will be optimized to achieve a balanced distribution of treatment assignment by stratifying randomization by baseline pterygium hyperemia grading [REDACTED]. [REDACTED] Subjects and study personnel, including but not limited to investigators, study staff,

central lab, clinical monitors, and designated staff within the Sponsor and the Sponsor's representatives, will remain masked to the study treatment assignments. There will be a small dedicated unmasked team comprised of Sponsor and Sponsor representatives that will manage IP supply, IRT services, and randomization schematics.

Figure 1. Study Flowchart

Upon DMC Review of Stage 1 Safety Data and Determination MTD, the study will move on to Stage 2.

[figure not shown]

Table 1. Schedule of Visits and Procedure for RMP-A03-001: Stage 1

Procedures	Screening Day -60 to -1 (Visit 1)	Baseline Day 1 (Visit 2)	Post-dose Day 1 (Visit 3)	Follow-up/Exit ¹ Day 7+1 day (Visit 4)
Informed Consent	X			
Inclusion/Exclusion	X	X		
Demographics	X			
Medical/Ophthalmic History	X	X		X
Concomitant Medications	X	X		X
Physical examination	X	X	X	X
Vital Signs	X	X	X	X
Urine Pregnancy Test ²	X	X		X
Clinical Labs	X			X
Adverse Events ³		X	X	X
Ocular Comfort Index	X	X	X	X
BCDVA	X	X	X	X
Intraocular Pressure	X	X	X	X
Slit Lamp Biomicroscopy	X	X	X	X
Indirect Ophthalmoscopy	X	X	X	X
Eyedrop Instillation Evaluation	X			
Study Drug Administration		X ⁴		
Study Drug Dispensing			X	
Study Drug Collected				X ⁵

¹ Every effort should be made to complete all Exit procedures at Early Termination

² A negative result on a urine pregnancy test before administration of study drug for women of childbearing potential is required for eligibility

³ AEs should be assessed before and after administration of study drug

⁴ First dose to be administered by in the clinic by study staff after completion of all Baseline assessments

⁵ Collect kit dispensed at Exit visit

Table 2: Schedule of Visits and Procedure for RMP-A03-001: Stage 2

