7.1.2 Baseline and Change from Baseline

Baseline is defined as the last non-missing observation obtained prior to the administration of the study drug. Change from baseline is defined as post-baseline result minus baseline result.

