7.3.1.1 Mixed Model with Repeated Measures (MMRM)

The treatment difference between the RMP-A03 and RMP-A03 vehicle treatment groups will be evaluated for the change from baseline pterygium hyperemia grading, with the RMP-A03 vehicle treatment group used as reference, using a MMRM. This analysis will use observed data for mITT Analysis Set.

The model will include terms for baseline pterygium hyperemia grading, treatment, visit, and the interaction of treatment and visit, with visit as a repeated measure and subject as random effect.

[REDACTED]

The least squares mean (LSM) and two-sided 95% confidence interval (CI) will be presented for treatment group, and visit. Additionally, the difference between each RMP-A03 treatment group and RMP-A03 vehicle treatment group will be calculated, along with the two-sided 95% CI.

The following is reference code for this analysis:

```
[REDACTED]
```

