8 CHANGE TO THE PLANNED ANALYSES FROM PROTOCOL

- Analyses of all efficacy endpoints will be performed using a model term for the actual baseline pterygium hyperemia grading as a continuous covariate, rather than the category used during stratification. Refer to Section 7.3 for details.

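### SAP 7.3.2 states no own-baseline covariate for change in pterygium length and corneal encroachment, so these secondary estimates are less precise than they need be

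*SAP*

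**What the plan says.** SAP 7.3.2 covers the secondary endpoints. Length and corneal encroachment are modelled: their changes "will be analyzed using the same ANCOVA and MMRM models as the primary analysis". Size at limbus is only tabulated by category, so this point does not concern it.

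The models referred to are in SAP 7.3.1. For the MMRM, "The model will include terms for baseline pterygium hyperemia grading, treatment, visit, and the interaction of treatment and visit". For the ANCOVA, "The model will include terms for treatment, and actual baseline pterygium hyperemia grading", entered as a continuous covariate. SAP 8 extends that term to every efficacy analysis: "Analyses of all efficacy endpoints will be performed using a model term for the actual baseline pterygium hyperemia grading as a continuous covariate", replacing the stratification category. No legible text names baseline length or baseline encroachment as a covariate.

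Three other places bear on the reading:

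- SAP 7.1.2 defines the outcome as a change score: "Change from baseline is defined as post-baseline result minus baseline result".
- SAP 3.2 describes "stratifying randomization by baseline pterygium hyperemia grading". Neither document names lesion size as a stratification factor.
- Protocol 9.8.1 lists two baseline terms for the primary MMRM, "baseline pterygium grading, and baseline pterygium hyperemia grading category used for stratification", and Protocol 9.8.2 adds, "The secondary endpoint will be analyzed in the same manner as for the primary endpoint". Neither section names the secondary endpoints' own baseline values.

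**The concern.** For the primary endpoint, baseline hyperemia grading is the outcome's own baseline, so that model is well specified. Carried over literally, the same term becomes the baseline of a different variable. The model for change in length would then contain no baseline length, and the model for change in encroachment no baseline encroachment.

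A change score is usually negatively correlated with its own baseline: eyes measured as large on Day 1 tend to be measured as smaller later, whatever the treatment. Without the own-baseline term, that predictable variation stays in the residual. With about 25 patients per arm, a chance difference in starting size also moves the estimated treatment effect. These two models carry the modelled part of the secondary objective, and both baseline values are already scheduled for collection on Day 1.

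**Working it through.** **The plan's own figure.** The power statement (Protocol 9.5, SAP 9) covers hyperemia only: 25 completers per arm, difference 0.66, SD 0.7, alpha 0.05, power about 90%. The standard error is 0.7 × sqrt(2/25) = 0.198, and 0.66/0.198 = 3.33. Normal-approximation power is Phi(3.33 - 1.96) = 91.5%; the noncentral t with 48 df gives 90.4%. The figure reproduces and does not depend on the secondary models.

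**Inputs for the secondary endpoints.** The documents give the design (three arms, about 25 each) and the change-score outcome. They give no SD, expected effect or correlation for length or encroachment. I therefore assume equal SD s at baseline and Day 28, a linear relation with correlation rho, and hyperemia grade unrelated to lesion size. Rho is shown as a range.

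**Formulas.**

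1. Residual variance of the change without own baseline: 2s²(1 - rho).
2. With own baseline as covariate: s²(1 - rho²).
3. Ratio of (2) to (1): (1 + rho)/2. The standard error of the treatment difference falls by 1 - sqrt((1 + rho)/2).
4. Equivalent sample size: 25 divided by (1 + rho)/2.
5. Expected shift of the unadjusted estimate when the active arm starts D larger than vehicle: -(1 - rho)D. With own baseline in the model it is 0.
6. For a D of one standard error, s × sqrt(2/25), that shift as a fraction of the unadjusted estimate's own standard error: sqrt((1 - rho)/2).

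| rho (assumed) | Variance ratio | SE reduction | Equivalent n per arm | Shift per unit D | Shift for a one-SE imbalance, in unadjusted SEs |
|---|---|---|---|---|---|
| 0.5 | 0.75 | 13.4% | 33.3 | -0.50 | 0.50 |
| 0.7 | 0.85 | 7.8% | 29.4 | -0.30 | 0.39 |
| 0.8 | 0.90 | 5.1% | 27.8 | -0.20 | 0.32 |
| 0.9 | 0.95 | 2.5% | 26.3 | -0.10 | 0.22 |
| 0.95 | 0.975 | 1.3% | 25.6 | -0.05 | 0.16 |

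As an illustration, a comparison with 80% power under the unadjusted model would have 89.9%, 86.0%, 84.0%, 82.0% and 81.0% down the rows.

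**The shift and the lost precision are one quantity.** (1) minus (2) is 2s²(1 - rho) - s²(1 - rho²) = s²(1 - rho)². Multiplied by 2/25, this is the variance of (1 - rho)D over randomisation. The wider interval already contains the shift, so the table's last two columns must not be counted as a harm on top of the SE column.

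**Simulation check.** Three arms of 25, size SD 1, a two-level hyperemia covariate, a single-visit ANCOVA and 6,000 runs per setting. Standard errors with hyperemia only against own baseline only:

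- rho 0.5: 0.287 against 0.249
- rho 0.7: 0.220 against 0.204
- rho 0.9: 0.127 against 0.123

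The slopes of the hyperemia-only estimate on the imbalance were -0.50, -0.29 and -0.10, close to formula 5. Hyperemia is a poor substitute: with a correlation of 0.3 between hyperemia (underlying scale) and size, and rho 0.5, the values were 0.282 and 0.248. Keeping both covariates costs almost nothing: 0.251 against 0.249 for own baseline alone at rho 0.5, with hyperemia unrelated to size.

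**The case against.** **The text may mean something better than it says.** Hyperemia is the primary endpoint's own baseline, so a reference to the same models could mean the same structure with each endpoint's own baseline substituted. A block after the MMRM terms and the reference code in SAP 7.3.1.1 and 7.3.1.2 are redacted and could show this. SAP 8 explains what replaces the stratification category; it does not say hyperemia is the only baseline term. All of this stands as a limit on certainty. A reader might infer that the SAP rules out own-baseline adjustment; the documents do not support that. The supportable statement is that the legible text does not provide for it, and SAP 7.3.2 shows no redaction in its modelling sentence.

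**Baseline is already used.** A reader might infer that chance imbalance goes uncorrected or that the estimate is biased. Neither follows. SAP 7.1.2 subtracts baseline in full, so the residual error is an over-correction in the opposite direction: half of D at rho 0.5, a tenth at rho 0.9. Over randomisation it averages to zero. SAP 7.3.2 also summarises baseline values by arm, so an imbalance would be visible.

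**Adjusting for hyperemia is reasonable.** It is the stratification factor, and SAP 7.3 explains that its actual value is used because patients were randomised on incorrect strata. This stands; the gap is the missing second term.

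**The gain may be small.** If lesion size is stable over 28 days, rho could be 0.9 or higher and the gain 1 to 3% of the standard error. This also stands. Against it, eligibility encroachment is judged by the investigator at the slit lamp (Protocol 5.3). If the endpoint is measured the same way, measurement error would lower rho, so a high value should not be presumed.

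**Conclusion.** The point holds as a precision gap in the stated models for two secondary endpoints. As visibly written, SAP 7.3.2 adjusts change in length and encroachment for hyperemia grading and states no own-baseline term. The estimates remain unbiased over randomisation, but they over-correct a chance imbalance by (1 - rho)D and have a larger standard error than necessary.

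The avoidable part of the standard error is about 13% at rho 0.5, 8% at 0.7, 2.5% at 0.9 and 1.3% at 0.95. These figures rest on equal variances, a linear relation and an assumed rho; nothing in the documents narrows the range. They apply to a Day 28 comparison at a single visit. In the MMRM, a single baseline slope shared by all visits would not guarantee the same gain at Day 28.

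The primary endpoint, type I error and the stated power are unaffected. No secondary result would be invalid. The correction is worth making because it uses data already planned and settles the covariate in writing instead of leaving it to inference from code.

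**What to change.** In SAP 7.3.2, state that the ANCOVA and MMRM for length and for encroachment each include that endpoint's own baseline value as a continuous covariate, with actual baseline hyperemia grading kept as a second covariate. In the MMRM, add the interaction of own baseline with visit, so that the slope at Day 28 is not constrained to equal the slopes at the other visits. Amend SAP 8 to list this addition, and check that the reference code agrees. If the code already contains these terms, only the text needs to change.

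Cost: one sentence in 7.3.2 and a matching edit in SAP 8. The ANCOVA gains one parameter. The MMRM gains one main effect plus three interaction terms for the four on-site post-baseline visits (Days 7, 28, 56 and 84), so 1 + 3 = 4. No new data are needed, and the primary analysis and sample size do not change.
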